3.5 Number of Subjects

[figure not shown]
Based upon an exploratory feasibility analysis of the Danish database, the incidence of adult ITP in this country is 3/100,000 per year. Extrapolating this rate to all 3 Nordic countries, there will be 570 newly registered ITP patients per year. Record collection of ITP patients began in 1996; therefore, by the end of 2008, there will be an estimated 7410 patients with ITP. Assuming that 80% of adult ITP patients will have durable remission, 1482 will become chronic ITP patients. This number is reduced to 1408 due to an expected 5% patient attrition over time. By 2008, these patients will constitute the group of prevalent cases eligible for romiplostim. Assuming that the Exposed Cohort will include 25% of the 1408 subjects, 352 patients with chronic ITP will be exposed to romiplostim during the first year post-approval.

For the period 2008 to 2018, there will be 5700 incident cases of adult ITP. Following the assumptions mentioned above, 1140 will become chronic, 1083 will remain after the attrition, and a total of 271 adult chronic ITP patients will receive romiplostim.

In total, there will be 623 patients (4234 patient-years) in the Exposed Cohort. According to the study design, the Unexposed Cohort for adult chronic ITP patients will include 1860 patients, which will account for 12,700 patient-years of follow-up ([Figure 1](#)). This is a conservative estimation; the sample size could be larger if the market share of romiplostim is larger than 25% percent.

The number of subjects for the romiplostim-off-label exposure is unknown.

Figure 1. Estimation of Study Sample Size

*Remission includes subjects considered "cured", including acute cases, cases that underwent successful splenectomy, and cases successfully treated with non romiplostim compounds.

3.6 Study Duration for Participants

The study period for the NCPRR will be from 01 January 2009 to 31 December 2019. Patients who receive romiplostim therapy between 01 January 2009 and 31 December 2018 will be selected into the patient registry. Similarly, unexposed patients will be included in the registry Unexposed Cohort between 01 January 2009 and 31 December 2018.

All subjects in the registry will be followed until the end-of-study period (31 December 2019), death, or loss to follow-up, whichever comes first. The specific romiplostim treatment follow-up time periods are defined in [Section 7.1](#).

4. SUBJECT ENROLLMENT

Subject enrollment is dependent on the NHRS. The NCPRR selects eligible study subjects to predefined study cohorts. The patient selection is based on diagnostic codes (ICD-10), medication, laboratory, BM, and pathological data.

4.1 Sub-Patient Group Identification

The adult chronic ITP study population is identified using diagnostic codes (ICD-10: D69.3-D69.4) for at least 6 months after the first primary ITP diagnosis, and as having received at least 1 ITP medication, and/or had a splenectomy procedure during this 6-month time period. Electronic medical records will be reviewed to confirm the diagnosis. Confirmation of the diagnosis of ITP will be carried out by clinical presentations and/or related treatment. Based upon the status of romiplostim therapy, these patients will be segregated into the Exposed Cohort and the Unexposed Cohort. The index date for patients in romiplostim Exposed Cohort is defined as the first date of receiving romiplostim therapy.

The Index Date in the exposed cohort will be the date of first exposure to romiplostim. A patient who has not been exposed to romiplostim will have an Index Date imputed based upon the date of diagnosis using 2 methods: 1) if the date of diagnosis is prior to 01 April 2009, the Index Date will be imputed as 01 April 2009 (the first date of romiplostim availability), and 2) if the date of diagnosis is 01 April 2009 or later, the date of diagnosis will be imputed as the Index Date.

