The exact sample size for the NCPRR is unknown, and is projected based upon the estimated national figure of adult chronic ITP patients, as well as the anticipated percentage of adult chronic ITP patients who may be treated with romiplostim. Based upon a conservative estimate, the study will have at least 623 adult chronic ITP patients who will receive romiplostim therapy during the study period, which will equate to more than 4,000 patient-years of follow-up. The NHRS of these 3 countries may also be capable of providing records for approximately 1,860 adult chronic ITP patients who are not exposed to romiplostim, which should provide more than 12,700 patient-years of follow-up data.

Summary of Subject Eligibility Criteria

The study population is chronic ITP patients, defined as those who have been diagnosed with ITP for more than 6 months, and who continually receive ITP treatments (eg, ITP medication), and/or have had a splenectomy procedure. Any adult (≥ 18 years) chronic ITP patient who has received at least 1 dose of romiplostim therapy, and who is registered in the NHRS of Denmark, Sweden, and Norway between 01 January 2009 and 31 December 2018, will be eligible subjects for this study. Patients will be continually followed up after discontinuation of romiplostim therapy.

Patients are excluded from the cohorts of chronic ITP patients if either of the following is present:

1. Any diagnosis of another condition associated with thrombocytopenia other than chronic ITP listed in [Appendix 2](#) at any time prior to or within 6 months after the qualifying diagnosis for chronic ITP. Examples of thrombocytopenia associated with other diseases and conditions include systemic lupus erythematosus (SLE), HIV infection, hepatitis C virus infection, malignancy, lymphoproliferative disorders, and myelodysplastic syndrome.
2. Lack of a platelet count below $150 \times 10^9/L$ without obvious cause in the 6 months before or after their first ITP diagnosis code

Comparison Group

Adult chronic ITP patients who are never exposed to romiplostim during the study period will be in the comparison group known as the romiplostim Unexposed Cohort. If patients in the comparison

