3.4 Selection of Participants (or Subject Eligibility)

3.4.1 Inclusion Criteria

Subjects in the NCPRR will be those whose health information is recorded by the NHRS of Denmark, Norway, or Sweden.

The eligible adult cITP romiplostim-exposed patients for the NCPRR must meet all of the following criteria:

- Patients must be 18 years or older at the time of chronic ITP diagnosis,
- Patients will have romiplostim therapy between 01 January 2009 and 31 December 2018, and
- Patients will have at least 6 months of medical information prior to initial date of receiving romiplostim treatment (Index Date), data from which will establish a baseline of study subjects.

The eligible adult cITP romiplostim-unexposed patients for the NCPRR must meet all following criteria:

- Patients must be 18 years or older at the time of chronic ITP diagnosis,
- Patients will not have received romiplostim therapy prior to or during the study period between 01 January 2009 and 31 December 2019, and
- Patients will have at least 6 months of medical information in the study period. The data from this period will establish baseline of subjects in the comparison group.

Eligible romiplostim-unexposed cITP patients will be the source of comparison cohorts for romiplostim-exposed cITP patients. Because potential confounding factors (eg, severity of ITP condition) may cause some biases for the study, however, robust propensity scoring and adjusted analyses will be essential ([Section 12](#)). In addition, appropriate contextualization from other recognized data sources will be used in comparisons to address selection biases.

In addition, according to initial dates of receiving romiplostim therapy among patients in the Exposed Cohort, the follow-up time period will be separated into 2 periods: (1) follow-up time period prior to romiplostim exposure, and (2) follow-up time period following romiplostim exposure. Patient experiences in the follow-up time period prior to the initial date of receiving romiplostim therapy will be considered as another “within-patient” comparison with the patient experiences during the follow-up time period after the initial date of receiving romiplostim therapy.

Eligible romiplostim Off-Label-Exposed patients will be any patient who received romiplostim therapy without an adult chronic ITP diagnosis.

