There are many factors that may affect the adult chronic ITP disease condition (eg, age, sex, length of disease, severity, platelet counts, splenectomy, co-morbidities, and concurrent medications). To reduce potential effects from confounding by indication of romiplostim therapy, a propensity score will be developed to create a pseudo-randomization in balancing important factors that might affect the outcomes between the romiplostim Exposed Cohort and Unexposed Cohort for chronic ITP patients. The propensity score is defined as the conditional probability of being treated given a set of important and relevant covariates. The logistic regression method will be used to develop the propensity score for the severity of the ITP condition. The variables to be considered may include, but are not limited to, age, sex, BMI/BSI, country, year of ITP diagnosis, length of disease, average platelet counts, lowest platelet counts, splenectomy, major comorbidities, and prior ITP medications (type and frequency), and frequency and severity of bleeding events. While the propensity score is being developed, other methods, such as stratification by country or by a span of years associated with changing practice patterns will be investigated. The aforementioned variables to be included in the propensity score development model will be updated and modified based upon the findings from an Amgen-sponsored historical study to be based upon the Danish Health Registry System Database for chronic ITP patients (Study 20070796) and expert opinions. The dependent variable for the model is romiplostim therapy (yes or no). The propensity model will be refined with every annual analysis based on newly available data. The propensity score will be reassigned to each patient for each annual analysis and the final analysis; therefore, the propensity-score for each subject in the cohorts reported in each annual and the final analysis may be different. However, variables involved in the propensity score development model will be the same throughout unless some new variable emerged during the 11-year study period. The data used to develop a propensity score will be from 6 months prior to the Index Date of receiving romiplostim therapy, and data from 6 months prior to the Index Date that is randomly selected from romiplostim-unexposed chronic ITP patients. To ensure the sensitivity and specificity of the propensity score, sensitivity analyses will be conducted for each established propensity model. The sensitivity and specificity test will be conducted using medical records for selected clinical characteristics, features, severity measures, and potential confounders.

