
The distribution of propensity scores for the Exposed Cohort and Unexposed Cohort will be graphically presented in a figure. Patients with very low or very high propensity scores whose scores are non-overlapping with patients in comparison cohorts will be excluded from (or trimmed from) the analysis. The “trimming” method will remove outliers from the analysis to reduce selection bias and the impact of patients with extreme conditions. This may impact the statistical power to evaluate any differences between the exposed and unexposed groups. A reduced sample size would reduce the probability of detecting a difference in a range of relative risks from 2 to 4 where the background incidence ranges from 0.5% to 5% (refer to [Appendix 1](#) for exact power). Based upon the distribution of propensity scores, 5 strata will be developed and used in the analysis. Propensity scores will also be used in multiple regression analysis as a covariate. Important variables including age, sex, ITP diagnostic year and disease duration that contribute to the propensity score can also be independently included in multiple regression analysis as additional covariates, which constitute a “Doubly Robust” model.

The propensity score, along with age, sex and diagnosis year will be used as needed to match the Exposed Cohort and Unexposed Cohort among adult chronic ITP patients.

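### Section 4.1 starts unexposed follow-up at ITP diagnosis, about six months before the patient can qualify as chronic ITP, and so puts the propensity-score window before diagnosis

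*Protocol*

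**What the plan says.** Protocol Section 4.1 gives two Index Date rules for never-exposed patients. For early diagnoses, "if the date of diagnosis is prior to 01 April 2009, the Index Date will be imputed as 01 April 2009". For the rest, "if the date of diagnosis is 01 April 2009 or later, the date of diagnosis will be imputed as the Index Date".

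The same section admits a patient to the chronic-ITP population on codes recorded "for at least 6 months after the first primary ITP diagnosis", together with "having received at least 1 ITP medication, and/or had a splenectomy procedure during this 6-month time period". The synopsis has the study population "defined as those who have been diagnosed with ITP for more than 6 months", with continuing treatment and/or splenectomy.

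The Index Date then does three jobs:

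- The glossary makes it the start of follow-up for the Unexposed Cohort.
- Section 7.3 counts time at risk from it.
- Section 12.3 takes propensity data from the six months before it. For the unexposed the wording is "data from 6 months prior to the Index Date that is randomly selected from romiplostim-unexposed chronic ITP patients".

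Two other sections describe a baseline differently. Section 3.4.1 requires of the unexposed that "Patients will have at least 6 months of medical information in the study period" and takes their baseline from that period. Section 7.1 defines a baseline period only as the six months before romiplostim, which a never-exposed patient does not have.

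After scoring, Section 12.3 trims patients with extreme scores "whose scores are non-overlapping with patients in comparison cohorts will be excluded from (or trimmed from) the analysis".

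**The concern.** Time zero should be a date on which the patient already belongs to the cohort, and baseline covariates should mean the same thing in both cohorts at that date. The second rule of Section 4.1 meets neither condition.

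First, covariates. Section 12.3 lists length of disease, splenectomy, prior ITP medication and bleeding among the candidate variables. For an unexposed patient indexed at diagnosis, the look-back window ends on the day ITP is first recorded. An exposed patient who is chronic at first dose has more than six months of disease, normally with treatment. The model would then separate the cohorts partly by how the Index Date was assigned and only partly by severity. Section 3.4.1 calls robust propensity scoring essential, so the main tool against confounding by indication is weakened.

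Second, person-time. The first six months after this Index Date are time that a patient must pass through in order to be in the cohort at all. Section 3.4.2 also excludes anyone with an Appendix 2 condition up to six months after the qualifying diagnosis, and Appendix 2 covers haematological malignancies, MDS and myelofibrosis. If the qualifying diagnosis is the Index Date, those outcomes cannot be counted in that period. For an exposed patient diagnosed more than six months before first dose, the exclusion window has already closed.

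**Working it through.** **Timeline.** Let D be the ITP diagnosis date, on or after 01 April 2009, for a never-exposed patient.

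- Index Date (4.1): D.
- Propensity window (12.3): D − 6 months to D, wholly before diagnosis.
- Earliest date at which the chronic definition can be met (4.1, synopsis): about D + 6 months.
- Start of follow-up and time at risk (glossary, 7.3): D, about six months before qualification.

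For diagnoses before 01 April 2009, the look-back from that date starts about 01 October 2008. Half of it lies before the study period opens on 01 January 2009, which does not fit the in-study baseline of 3.4.1.

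**Reproducing the projected cohort (Section 3.5).**

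- Prevalent: 570 × 13 = 7410; × 0.20 = 1482; × 0.95 = 1408. Exposed 25% = 352; unexposed 1408 − 352 = 1056.
- Incident: 5700 × 0.20 = 1140; × 0.95 = 1083. Exposed 25% = 271; unexposed 1083 − 271 = 812.
- Totals: 352 + 271 = 623 exposed, as stated; 1056 + 812 = 1868 unexposed, against 1860 stated.

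The 12,700 unexposed patient-years cannot be rebuilt, because follow-up by group is not given. They are taken as stated.

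**Share affected.** Assume that incident diagnoses are uniform over 2009 to 2018. Then 117 of 120 months (97.5%) fall on or after 01 April 2009. 812 × 0.975 ≈ 792, and 792/1868 = 42%. Patients diagnosed from October 2008 to March 2009 have a window partly before diagnosis: 570 × 0.5 × 0.20 × 0.95 × 0.75 ≈ 41, or 2%.

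**Person-time before qualification.**

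- Indexed at diagnosis: 792 × 0.5 = 396 patient-years.
- Diagnosed October 2008 to March 2009, on average 0.25 years short of qualifying on 01 April 2009: 41 × 0.25 ≈ 10.
- Total: about 406; 406/12,700 = 3.2%.
- Among incident unexposed patients, diagnosis uniform over 2009 to 2018 and follow-up to the end of 2019 give a mean of 6.0 years, so 0.5/6.0 = 8.3%.
- If the pre-romiplostim time of the 271 incident eventual users were also counted from diagnosis: 1083 × 0.975 × 0.5 = 528; 528/12,700 = 4.2%.

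**Effect on a rate.** For an outcome that cannot be counted in this time, removing 406 patient-years raises the unexposed rate by 12,700/(12,700 − 406) = 1.033.

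**The case against.** The best defence is that date of diagnosis means the date on which chronic ITP is established. Sections 3.4.1 and 3.4.2 do speak of a chronic ITP diagnosis and a qualifying diagnosis. On that reading the pre-diagnosis window and the early follow-up disappear. But Section 4.1 itself names only the ITP diagnosis, and nothing in the protocol says how a chronic diagnosis is dated. Even so read, disease duration at Index would be a near-constant six months in incident unexposed patients, and the 01 April 2009 rule would still reach back before the study period.

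Several stronger readings are tempting, and the document does not support them:

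- A reader might infer that trimming removes every patient indexed at diagnosis. Section 12.3 also lists age, sex, BMI/BSI, country, year of diagnosis, platelet counts and comorbidities, so overlap depends on the fitted model. The share trimmed cannot be computed from the protocol.
- A reader might say that the window precedes the disease. It precedes the diagnosis; low platelet counts or bleeding may already be on record.
- A reader might take Section 12.3 as a third, random index rule. The sentence can equally mean that data are sampled from unexposed patients indexed under 4.1. It is unclear rather than a proven contradiction.
- A reader might treat all early follow-up as event-free. Thrombosis and bleeding can still occur and be counted. The guaranteed part concerns death, which is not a listed endpoint, and Appendix 2 conditions.

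The glossary measures length of disease up to the study event and not up to Index. That value depends on later follow-up and cannot come from a pre-Index window; disease duration at Index is zero under the rule either way.

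The protocol also offers Cox models with time-varying exposure, stratification by time since diagnosis and a within-patient comparison. It admits that overlap may be poor and labels all comparisons exploratory. This limits the harm, but none of it corrects time zero or the covariate window.

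**Conclusion.** The defect holds as a matter of text. About 42% of the projected Unexposed Cohort would be indexed some six months before they can qualify, with propensity covariates drawn wholly from before diagnosis. The main damage is to the comparability of the propensity score; its size, including the number trimmed, is not quantifiable from the protocol. The person-time effect is small: about 3% of unexposed patient-years overall and about 8% among incident unexposed patients. It matters chiefly for AML, MDS and myelofibrosis, and there only if the qualifying diagnosis is the Index Date.

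The unexposed rates and the exploratory comparisons are affected. The primary objective, an incidence rate in patients receiving romiplostim, is not, because the exposed Index Date is the first dose. The figures rest on the Section 3.5 projection, on uniform accrual, and on reading diagnosis in Section 4.1 as the ITP diagnosis.

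**What to change.** State one Index Date rule for the unexposed and use it alike in Sections 3.4.1, 4.1, 7.1, 7.3 and 12.3:

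- The Index Date is no earlier than the date the chronic-ITP criteria are met. Patients who have not met them by 01 April 2009 take their later qualification date.
- Time at risk starts there.
- Propensity covariates come from the six months before that date in both cohorts, and the wording on random selection in 12.3 is rewritten to say what is sampled.
- Section 3.4.2 says which diagnosis is the qualifying one. If it is the chronic one, the six-month exclusion would run past the new Index Date.

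Disease duration at Index would still be a near-constant six months in incident unexposed patients. Risk-set sampling of Index Dates, matched on time since diagnosis, may therefore be considered, but for the comparative analyses only. The descriptive rates should keep all qualified unexposed person-time.

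The cost is about 3% of unexposed patient-years, plus rewording and programming. No new data are needed.

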5. DATA COLLECTION PROCEDURES

5.1 Primary Data Collection

The primary data collection for the NCPRR is dependent upon the NHRS. All citizens in Denmark, Sweden, and Norway are included in the systems, and all health care information for each citizen will be included in the system databases. For this reason the NCPRR will not need to actively collect data directly from patients.

Patients with a NHRS diagnosis of ITP of 6 months duration or more are selected for abstraction of medical records and collection of details of the medical history including romiplostim exposure. If a patient was not seen in hospital (in-patient or out-patient

contact, including hematology clinic visits) at least once during the reporting period, the charts for that patients for that reporting period will not be reviewed. When the patient re-appears in the hospital database in following reporting periods, the chart abstraction will resume for that patient.

Because ITP is a diagnosis of exclusion and secondary causes of thrombocytopenia may be difficult to diagnose, some patients will require review of medical records and laboratory data including bone marrow exams, if any, prior to their first diagnosis of ITP (ICD-10: D69.3-D69.4). These will include the relevant time periods prior to their first diagnosis of ITP for all patients who have a history of any condition from [Appendix 2](#) prior to the first diagnosis of ITP.

5.2 Case Ascertainment for Clinical Events

Clinical events (eg, bleeding, thromboembolic, and hematological malignancy endpoints) will be identified and ascertained by ICD-10 diagnostic codes and/or relevant laboratory and pathology data. The detailed diagnostic codes will be provided by the study statistical analysis plan (SAP). All identified cases will be confirmed using electronic medical record review that will be blinded to romiplostim exposure. Patients observed with one of the outcomes of interest during the study will be continually followed for other outcomes until the end of study, death, or loss to follow-up, whichever comes first.

